## **5 STUDY OBJECTIVES**

### **5.1 Primary Objective**

The study’s *primary efficacy endpoint* will be the proportion of responders at the end of treatment, after up to 24 weeks/6 months to 72 weeks/18 months of treatment, defined as 50% or greater hair re-growth from baseline as assessed by SALT at week 24 to 72. This is a relatively strict definition for defining responders and non-responders and was chosen to minimize the potential for spontaneous remission, in which fewer than 10% are expected to achieve this magnitude of hair regrowth spontaneously.

The duration of treatment will be up to 6 to 18 months, at the discretion of the investigator, dependent on individual subject response as well as safety considerations.

To assess the durability of responses, patients who achieve 50% regrowth from baseline during the first 6 to 18 months, will continue to be followed for an additional 6 months off treatment or until it is determined that relapse has occurred.

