------------------------	--

Study Objectives: Primary: Secondary:	
The study's primary efficacy endpoint will be the proportion of responders at the end of treatment, which may be up to between 24 weeks/6 months to 72 weeks/18 months of treatment, with response defined as 50% or greater hair re-growth from baseline as assessed by SALT score at the end of treatment - week 24 to 72. This is a relatively strict definition for defining responders and non-responders and was chosen to minimize the potential for spontaneous remission, in which fewer than 10% are expected to achieve this magnitude of hair regrowth spontaneously.
 
As additional secondary endpoints, efficacy will be measured by changes in hair re-growth as a continuous variable as determined by physical exam and Canfield photography, as well as patient and physician global evaluation scores. To assess the durability of responses, patients will continue to be followed for an additional 6 months after treatment is completed. Response at the end of study, week 72-96, will be examined as a secondary outcome. We will compare the efficacy of tofacitinib in promoting hair regrowth in patients with moderate to severe patch type alopecia areata to the efficacy in treating patients with current alopecia totalis (AT) or universalis (AU).

Study Design:	
Open-label pilot study of tofacitinib 5mg to 10mg PO BID, for 6 to 18 months in the treatment of moderate to severe AA, and alopecia totalis or universalis, followed by 6 months follow-up off drug to assess for delayed response to treatment and/or the incidence and timing of recurrence of disease.
 
The initial treatment dose will be tofacitinib 5mg PO BID, and may be increased up to 10mg PO BID, if clinically indicated at the discretion of the investigator.
 
The initial treatment duration will be 6 months, and may be extended by up to 12 additional months if clinically indicated with an acceptable lab safety profile, at the discretion of the investigator.

Study Schema Drugs / Doses / Length of Treatment)	
Tofacitinib (5 mg to 10 mg) will be taken orally twice a day for up to 24 to 72 weeks.
 
Study drug dose may be reduced and/or temporarily discontinued if indicated based upon laboratory values.

Accrual Goal: (Total number of subjects)	15

Accrual Rate: (Number of subjects expected per month)	1-3

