#### *Secondary efficacy outcomes in detail*

1. Percent hair regrowth from baseline determined by SALT measurements following end of treatment (at 24 to 72 weeks) and during the observational phase at 8, 16, and 24 weeks after end of treatment.

2. Comparison of the proportion of responders in the experimental group with the historically known placebo response rate (<10%), with response defined as 50% change in SALT score (50% regrowth) from baseline, at end of treatment (week 24 to 72), and at the end of study (8, 16, and 24 weeks after end of treatment).
3. Comparison of the proportion of subjects in each group attaining global overall improvement SALT score of A5 (100% coverage) supported by ≤ SALT 25 at the end of treatment (week 24 to 72), and at the end of study (8, 16, and 24 weeks after end of treatment).
4. Change in PGA (Physician Global Assessment) based on live evaluations and evaluation of standardized photographs between baseline, and each subsequent visit during the treatment period and the follow up period.
5. Change in patient global assessment between baseline, and each subsequent visit during the treatment period and the follow up period.
6. Change in patient quality of life assessment from baseline compared to subsequent visits during the treatment period and the follow up period.
7. Frequency of occurrence and timing of relapse (as defined above) in responders followed for 6 months off therapy.
8. Safety will be evaluated as a secondary endpoint using descriptive statistics to summarize the cumulative incidence and types of AEs.
9. The proportion of patients who discontinued treatment will be summarized.

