## 11 EFFICACY ASSESSMENT

### 11.1 Primary Efficacy Assessment

The study's *primary efficacy endpoint* will be the proportion of responders after 6 months of treatment, with response defined as 50% or greater hair re-growth from baseline as assessed by SALT score (Figure 6) at week 24. This is a relatively strict definition for defining responders and non-responders and was chosen to minimize the potential for spontaneous remission, in which approximately 8% or less are expected to achieve this magnitude of hair regrowth spontaneously.

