# **13 STATISTICAL CONSIDERATIONS**

## **13.1 Sample Size Determination**

Based on two recently completed randomized trials (Price et al, 2008; Strober et al, 2009) in similar patient populations (moderate to severe AA) we expect placebo response rates to be between 6% (>50% improvement in SALT score) and 12% (>25% improvement). We have chosen our primary endpoint conservatively (proportion of patients with >50% improvement in SALT index) as a relatively strict criteria that should minimize placebo response rates to 10% or less (0-1 of 10 subjects). This allows a higher degree of confidence that appreciable response rates are attributable to drug rather than spontaneous remission.

With our sample of n=15, we will have greater than 80% power to reject the null hypothesis that the true underlying remission rate is 10% if we observe a rate in our sample of 48%, holding type I error to 5%. If we assume that the underlying remission rate is 30%, then we have greater than 80% power to reject that null hypothesis if the observed rate is 73% or above, again holding type I error to 5%.

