### 13.3 Endpoint Definitions

1. The study's *primary efficacy endpoint* will be the proportion of responders after 6 to 18 months of treatment, with response defined as 50% or greater hair re-growth from baseline as assessed by SALT score at week 24 to 72.

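### Section 11.1 reads the primary response at week 24 and the other sections read it at week 24 to 72, against a historical rate below 10% with no stated observation time

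*Combined protocol and SAP*

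**What the plan says.** **Read time of the primary endpoint.** Section 11.1 says the endpoint "will be the proportion of responders after 6 months of treatment, with response defined as 50% or greater hair re-growth from baseline", and fixes the SALT reading at week 24. The synopsis has response "assessed by SALT score at the end of treatment - week 24 to 72", and section 5.1 also reads it when treatment ends. Section 13.3 defines the endpoint as "the proportion of responders after 6 to 18 months of treatment, with response defined as 50% or greater" regrowth, at week 24 to 72; it does not say that the reading is taken at the end of treatment.

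**What sets the read time.** Treatment lasts six to 18 months, "at the discretion of the investigator, dependent on individual subject response as well as safety considerations" (section 5.1).

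**Benchmark.** Section 11.1, beside week 24, says "approximately 8% or less are expected to achieve this magnitude of hair regrowth spontaneously". Section 5.1, beside week 24 to 72, says "fewer than 10% are expected to achieve this magnitude of hair regrowth spontaneously". Section 13.1 says "we expect placebo response rates to be between 6" and 12 per cent, the lower figure being for more than 50% improvement, and attributes this to two randomized trials. No section gives the length of observation behind the 6%, 8% or below-10% figures. Item 2 of the secondary outcomes (sections 5.2, 11.1.1 and 13.3) is "Comparison of the proportion of responders in the experimental group with the historically known placebo response rate" of less than 10%, at end of treatment and at three later visits.

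**Analysis.** Section 13.4.3 plans descriptive summaries, intended to give an effect size for designing later trials. It has no decision rule.

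**The concern.** The trial has one arm, so the historical rate is the main guard against taking spontaneous regrowth for drug effect. That guard works only if the rate and the trial reading cover similar lengths of time. Here the plan gives two reading rules, one of them with a time that depends partly on how the subject is responding. Nearly the same spontaneous rate is placed beside a 24-week reading and beside one that may come at three times that duration.

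Two things are at stake. First, it is unclear which proportion is the trial's primary result, and either could be presented as primary once the open-label results are known. Second, a proportion read late in some subjects may be set against a rate observed over a shorter time, and then passed on as the effect size for later trials.

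**Working it through.** **1. The definitions side by side.**

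| Place | Reading |
|---|---|
| Section 11.1 | week 24 |
| Synopsis; section 5.1 | end of treatment, week 24 to 72 |
| Section 13.3 | week 24 to 72, no visit named |

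Two other places keep the six-month frame: section 9.1 labels week 24 as the end of treatment, and section 11.1.1 defines nonresponders by six months of treatment. A subject below 50% at week 24 who is extended and later reaches 50% counts as a nonresponder under section 11.1 and as a responder under end-of-treatment reading. With n = 15, each such subject moves the proportion by 1/15 = 6.7 points.

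**2. The plan's own power figure.** Section 13.1 claims more than 80% power with n = 15 and 5% type I error, for 10% against 48% and for 30% against 73%. With an exact one-sided binomial test:
- Null 10%: P(X≥4) = 0.0556 and P(X≥5) = 0.0127, so the cutoff is 5 of 15. Power at 48% is 92.0%.
- Null 30%: P(X≥8) = 0.0500, just above 5%, and P(X≥9) = 0.0152, so the cutoff is 9 of 15. Power at 73% is 91.8%.

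The claim reproduces. The arithmetic of the sample size is not the problem.

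**3. What a bias towards the drug requires.** Two conditions must both hold.
- Some week-24 nonresponders are extended. If only responders are extended, the end-of-treatment proportion cannot exceed the week-24 proportion. Section 4 justifies longer treatment by patients who need it to respond fully, which suggests that incomplete responders are extended, but no section says who is.
- The benchmark covers a shorter period than the actual readings. If it already covers about 72 weeks, there is no inflation from elapsed time.

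**4. Illustration.** Assumptions, none of them in the documents: the benchmark r of 6–10% is a 24-week rate, the hazard is constant, regrowth is not lost, and all 15 subjects can remit. Then the no-drug rate by week 72 is q = 1 − (1 − r)³. If half of the week-24 nonresponders are extended to week 72, the rate is r + 0.5(q − r). The last three columns give P(X≥5 of 15) without any drug effect.

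| r | q | Rate, half extended | None extended | Half extended | All extended |
|---|---|---|---|---|---|
| 6% | 16.9% | 11.5% | 0.1% | 2.2% | 9.5% |
| 8% | 22.1% | 15.1% | 0.5% | 6.3% | 22.3% |
| 10% | 27.1% | 18.6% | 1.3% | 12.9% | 38.4% |

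The no-drug proportion rises by 11–17 points if all are extended and by 5–9 points if half are.

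**5. How far other assumptions reduce this.** P(X≥5) for r from 6% to 10%, all nonresponders extended:
- Only 10 patch-type subjects can remit (section 1.1.1 says totalis and universalis seldom do): 1.7–10.5%. Only 8 can: 0.5–3.8%. The plan does not fix this split.
- The hazard halves every 24 weeks, so q = 1 − (1 − r)^1.75: 1.4–9.3%.
- A quarter of responders lose response before the reading: 3.3–17%. Half do: 0.6–4.2%.
- The benchmark is a 48-week rate, so q = 1 − (1 − r)^1.5: 0.8–5.6%.
- The benchmark is a 72-week rate: 0.1–1.3%, that is, no inflation.

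**The case against.** Three of the four statements give week 24 to 72, and section 11.1 may simply not have been updated when the extension was added. That is plausible, and correcting section 11.1 alone would remove the contradiction. But it is current text under the heading that defines the primary assessment, and nothing says which section governs.

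On the benchmark the opposing case is stronger, and it limits what can be claimed:
- The documents do not say that nonresponders are extended.
- Section 4 says that spontaneous remission in extensive disease is usually incomplete and confined to a minority of scalp areas. This argues against 50% regrowth continuing to accrue at a constant rate.
- Safety stops, or loss of regrowth before the reading, could work against the drug.
- The synopsis and section 13.1 also give a null of 30%, above the illustrated maximum of 27%. The chance of reaching its cutoff of 9 of 15 stays below 1% at every illustrated rate. However, that null is only a power scenario and is undated too, while the comparison listed in item 2 is with less than 10%.

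A reader might infer three stronger claims that the documents do not support:
- That the trial has a 38% false-positive risk. This figure belongs to a test that the analysis section does not contain, under the most unfavourable of the assumptions in step 4.
- That the comparisons at 8, 16 and 24 weeks after treatment also favour the drug. Those readings are off drug, where relapse lowers the proportion. The benchmark is undated there as well, but the direction is not shown.
- That the one-third remission within a year in section 1.1.1 is the proper benchmark. It describes patchy disease at presentation, not this population.

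**Conclusion.** The contradiction in the primary read time is certain and needs no assumption: section 11.1 cannot stand with the synopsis and section 5.1, and section 13.3 leaves the visit open. Each subject who first reaches 50% after week 24 and holds it at end of treatment is worth 6.7 points.

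The mismatch with the benchmark is also real, since the read time depends partly on response and no observation time is given for the historical rate. Bias towards the drug is conditional on both requirements in step 3, and the documents establish neither. Its size therefore cannot be derived from them; the illustrations run from no inflation to a no-drug rate of 27% by week 72.

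Because the analysis is descriptive, what is affected is the reported proportion, the listed comparison with less than 10%, and the effect size passed to later trials. No formal test is affected.

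**What to change.** 1. State one primary definition in identical words in the synopsis and sections 5.1, 11.1 and 13.3. Make the six-month wording in sections 9.1 and 11.1.1 consistent with it.
2. Whichever read time is primary, report the week-24 SALT responder proportion for all treated subjects and use it for the comparison in item 2 of the secondary outcomes. Alternatively, state the observation time behind the 6%, 8% and below-10% rates and compare only at a matching time. Keeping end of treatment as primary is compatible with either route.
3. Report end-of-treatment and post-treatment response descriptively, with exact confidence intervals.
4. Report the week-24 and end-of-treatment proportions together, with the date and reason for the change in read time, because section 4 refers to experience already gained in this study.

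Cost: a protocol amendment, which needs IRB approval before use (section 14.1). No visits or patients are added, since SALT is already scheduled at week 24 for every subject (section 9.1 and Table 3), and treatment duration is unchanged. The drawback is that responses first appearing after week 24 do not count in a week-24 benchmark comparison, although section 4 expects some patients to need longer. They remain in the end-of-treatment outcome.

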### **5.2 Secondary Objectives**

As secondary endpoints, safety and additional efficacy outcomes will be assessed. Additional efficacy outcomes will be measured by changes in hair re-growth as a continuous variable as determined by physical exam and Canfield photography, as well as patient and physician global evaluation scores. To assess the durability of responses, patients who achieve 50% reduction in baseline SALT score will continue to be followed for an additional 6 months off treatment or until it is determined that relapse has occurred.

#### *Secondary efficacy outcomes in detail*

1. Percent hair regrowth from baseline determined by SALT measurements following end of treatment (at 24 to 72 weeks) and during the observational phase at 8, 16, and 24 weeks after end of treatment.

2. Comparison of the proportion of responders in the experimental group with the historically known placebo response rate (<10%), with response defined as 50% change in SALT score (50% regrowth) from baseline, at end of treatment (week 24 to 72), and at the end of study (8, 16, and 24 weeks after end of treatment).
3. Comparison of the proportion of subjects in each group attaining global overall improvement SALT score of A5 (100% coverage) supported by ≤ SALT 25 at the end of treatment (week 24 to 72), and at the end of study (8, 16, and 24 weeks after end of treatment).
4. Change in PGA (Physician Global Assessment) based on live evaluations and evaluation of standardized photographs between baseline, and each subsequent visit during the treatment period and the follow up period.
5. Change in patient global assessment between baseline, and each subsequent visit during the treatment period and the follow up period.
6. Change in patient quality of life assessment from baseline compared to subsequent visits during the treatment period and the follow up period.
7. Frequency of occurrence and timing of relapse (as defined above) in responders followed for 6 months off therapy.
8. Safety will be evaluated as a secondary endpoint using descriptive statistics to summarize the cumulative incidence and types of AEs.
9. The proportion of patients who discontinued treatment will be summarized.

## **6 ETHICAL CONSIDERATIONS**

### **6.1 Good Clinical Practice**

This study will be conducted in accordance with Good Clinical Practice (GCP), as defined by the International Conference on Harmonization (ICH) and in accordance with the ethical principles underlying European Union Directive 2001/20/EC and the United States Code of Federal Regulations, Title 21, Part 50 (21CFR50).

The study will be conducted in compliance with the protocol. The protocol, any amendments, and the subject informed consent will receive Institutional Review Board/Independent Ethics Committee (IRB) approval/favorable opinion before initiation of the study.

All potential serious breaches must be reported immediately. A serious breach is a breach of the conditions and principles of GCP in connection with the study or the protocol, which is likely to affect, to a significant degree, the safety or physical or mental integrity of the subjects of the study or the scientific value of the study.

Study personnel involved in conducting this study will be qualified by education, training, and experience to perform their respective tasks. This study will not use the services of study personnel where sanctions have been invoked or where there has been scientific misconduct or fraud (e.g., loss of medical licensure; debarment). Systems with procedures that ensure the quality of every aspect of the study will be implemented.

## **6.2      Institutional Review Board/Independent Ethics Committee**

Before study initiation, the investigator must have written and dated approval/favorable opinion from the IRB for the protocol, consent form, subject recruitment materials/process (e.g., advertisements), and any other written information to be provided to subjects. The investigator should also provide the IRB with a copy of the Investigator Brochure or product labeling, information to be provided to subjects, and any updates. The investigator should provide the IRB with reports, updates, and other information (e.g., expedited safety reports, amendments, and administrative letters) according to regulatory requirements or institution procedures.

## **6.3      Informed Consent**

Investigators must ensure that subjects are clearly and fully informed about the purpose, potential risks, and other critical issues regarding clinical studies in which they volunteer to participate. Freely given written informed consent must be obtained from every subject before clinical study participation, including informed consent for any screening procedures conducted to establish subject eligibility for the study.

The rights, safety, and well-being of the study subjects are the most important considerations and should prevail over interests of science and society.

# **7            INVESTIGATIONAL PLAN**

## **7.1      Study Design and Duration**

**Screening:** A complete medical history will be taken. Patients will be screened for pre-existing renal (basic metabolic and urine analysis), hematologic (CBC with differential and reticulocytes) or hepatic dysfunction; lipid panel; prior exposure to tuberculosis (PPD and or quantiferon test) or hepatitis; pregnancy tests will be done in women of childbearing potential.

**Assessments:** Baseline assessments of disease severity will be done. This will include SALT score (Severity of Alopecia Tool, Addendum 1), Physician global assessment (PGA), patient global assessment and patient quality of life assessment. In order to minimize or eliminate inter-rater variability, every effort will be made to have the same investigator evaluate an individual subject at each visit. Whenever possible the same investigator (the PI or her designee) will examine the patient's scalp, determine the SALT score, and grade the photographic images.

### **Visit Schedule and Assessments**

Screening assessments and all scheduled study visits are outlined in the Table of Study Assessments, Addendum 2.

#### **Baseline to Week 24 (period on study medication)**

Patients will be seen at baseline, and at weeks 4, 8, 12, 16, 20 and 24 weeks. Assessments of disease severity will be performed via physical exam and photography and will be objectively quantified using the SALT, Physician global assessment (PGA) at baseline, and weeks 4, 8, 12, 16, 20, and 24, and patient global assessment and patient quality of life assessment at baseline and weeks 12 and 24.

PGA and patient evaluations will be based on similar 100mm visual analog scales with 0 labeled as no scalp hair loss and 100 labeled as complete scalp hair loss. Patients and physicians will place a vertical mark along the horizontal line depending on their assessment of the degree of hair loss present at the time of assessment.

Patient quality of life assessments will be based on changes in the Dermatology Life Quality Index DLQI, which we have previously used for patient evaluation in the AA registry, and the Skindex-29 Questionnaire.

Photography will be performed at baseline and weeks 4, 8, 12, 16, 20, and 24; skin biopsies will be performed at baseline and weeks 4 and 24; blood draws for safety parameters and immune studies will be done based on the attached table of study procedures.

Optional additional biopsies and blood draws may be obtained at the investigator's discretion and with the subject's permission as indicated by clinical considerations such as variation in the timeline to regrowth from one subject to another, focal apparent resistance to treatment, as well as other potential unpredictable clinical occurrences. Unscheduled biopsies and blood draws will ensure that tissue and blood samples can be obtained at optimal time points to evaluate the changes occurring in response (or lack of response) to treatment. The patient will be given the option to agree to, or decline, the additional biopsies and blood draws.

Adverse events will be assessed at every visit.

